2.4. Treatment Assignment and Masking

At the Baseline visit, patients meeting all study criteria will be stratified by disease duration (<5 or 5+ years) and baseline MGS score in the study eye (<6 or 6-≤12). Patients will be randomized in a 1:1:1 ratio, within each of the 4 strata, to AZR-MD-001 0.5%, AZR-MD-001 1.0%, or placebo. The interactive web response system (IWRS) system will provide both a patient randomization number and study kit number to use for that patient.

Patients will be dispensed Vaseline (in a separate kit from study kit, and identified by a Vaseline kit number), and will administer it while onsite during the Baseline visit. Patients demonstrating the ability to correctly apply the ointment will be randomized and subsequently dispensed the

study kit (AZR-MD-001 0.5%, AZR-MD-001 1.0%, or placebo), to be administered twice weekly at home. All study kit medication will be provided in identical tubes and cartons to maintain masking of the study. The placebo packaging was designed to have the same appearance as the AZR-MD-001 treatment.

Upon database freeze, a designated team (as described in the [AZ201801 Expansion Cohort Unmasked Data Access Plan](#)) will be unmasked in order to conduct the Month 3 analyses, and those team members will not participate in study execution after unmasking. The remainder of the study personnel will be unmasked after all patients have completed Month 6, and the database has been locked.

2.5. Administration of Study Medication

Vaseline will be administered while at the study site, during the Baseline visit.

Subsequently, patients (or a caregiver) will apply a dose of approximately 5 mg for each application of the randomized study treatment, applied twice weekly in the evenings as described in [AZ201801 Protocol Section 6.1.3](#).

Multi-dose tubes of the masked study medication are each to be used for only 30 days for both eyes. The number of used tubes, unused returned tubes, and unreturned tubes will be recorded at subsequent visits.

2.6. Study Procedures and Flowchart

[Table 2](#) provides the schedule of activities.

Table 2 Schedule of Activities

Study Period	Qualification		Double-Masked Period				
	Three Month Efficacy Evaluation			Safety Follow-Up			
	Screening ^a (Day -14)	Baseline Day 0 Randomization	Day 14	Month 1.5	Month 3	Month 4.5	Month 6
Visit Window	± 2 Days	N/A	± 2 Days	± 7 Days	± 2 Days	± 7 Days	± 2 Days
Informed consent/authorization	X						
Contact IVRS/IWRS for patient number assignment (screening number)	X						
Demographics (including height and weight)	X						
Inclusion/exclusion criteria	X	X					
Medical and ophthalmic history	X	X					
Medication history	X						
Washout medications	X						
Vital signs (pulse rate, blood pressure)	X	X			X		X
Pregnancy test (urine) for female patients ^b	X						
Patient Ocular Symptoms (VAS)	X	X	X	X	X	X	X
OSDI	X	X	X	X	X	X	X
SPEED	X	X	X	X	X	X	X
BCVA	X ^c	X	X	X	X	X	X
Slit-lamp biomicroscopy (includes eyelid margin erythema/telangiectasias)	X	X	X	X	X	X	X
TBUT ^d	X	X	X	X	X	X	X
Sodium fluorescein corneal staining, Oxford scale	X	X	X	X	X	X	X
Lissamine green conjunctival staining, Oxford scale	X	X	X	X	X	X	X

Study Period	Qualification		Double-Masked Period				
	Three Month Efficacy Evaluation			Safety Follow-Up			
	Screening ^a (Day -14)	Baseline Day 0 Randomization	Day 14	Month 1.5	Month 3	Month 4.5	Month 6
Visit Window	± 2 Days	N/A	± 2 Days	± 7 Days	± 2 Days	± 7 Days	± 2 Days
MGE ^d	X	X	X	X	X	X	X
Schirmer without anesthesia	X	X			X		X
IOP	X				X		X
Ophthalmoscopy exam ^e	X				X		X
Meibography	X				X		X
Adverse events/medications/procedures	X	X	X	X	X	X	X
Discontinue concomitant medication(s) impacting inclusion/exclusion	X						
Contact IVRS/IWRS for patient randomization number		X					
Medication dispensing/return		X		X	X	X	X
Physician Observation of Drug Application		X					

Abbreviations: BCVA = best-corrected visual acuity; DED = dry eye disease; IOP = intraocular pressure; MGD = meibomian gland dysfunction; MGE = meibomian gland evaluation; OSDI = ocular surface disease index; SPEED = standard patient evaluation of eye dryness; TBUT = tear break-up time; VAS = visual analogue scale.

^a Screening diagnostic procedures are not required to be performed on the same day, and can be performed across multiple days from days -14 to -2. At screening, patients will be asked to report use of artificial tears and all other treatments for MGD and/or DED. Patients should wash out from all medication listed in the inclusion/exclusion criteria. Patients who are re-enrolled following an initial screen failure will receive a new screening number.

^b For females of childbearing potential.

^c Manifest refraction performed at screening will be used at each visit to obtain BCVA.

^d TBUT and MGE should be performed by the same individual for a given patient. The individual performing the measurement will not be involved in drug dispensing or accountability and should remain masked to the treatment received by the patient.

^e Ophthalmoscopy examination will be dilated at screening and undilated for study exit unless dilation is necessary.

3. ENDPOINTS

3.1. Efficacy Endpoints

3.1.1. Primary Efficacy Endpoints

Primary efficacy measures are divided into endpoints for primary efficacy signs and primary efficacy symptoms for MGD.

- The primary efficacy sign for MGD is the Change from Baseline at Month 3 in MGYLS (0 to 15 scale; higher scores are better).
- The primary efficacy symptom for MGD is the Change from Baseline at Month 3 in OSDI total score (0 to 100 scale; lower scores are better).

3.1.2. Secondary Efficacy Endpoints

The key secondary efficacy endpoints include:

- MGYLS
 - Proportion of patients with a change from baseline in MGYLS score ≥ 5 at Day 14, Month 1.5, and Month 3
- OSDI
 - Proportion of patients with OSDI total score < 13 at Day 14, Month 1.5, and Month 3.
- SPEED
 - Change from Baseline at Day 14, Month 1.5, and Month 3 in SPEED.
- Eye Dryness Visual Analogue Scale (VAS)
 - Change from Baseline at Day 14, Month 1.5, and Month 3 for Eye Dryness VAS.

The secondary efficacy endpoints include:

- MGS (0 to 45 scale; higher scores are better)
 - Change from Baseline at Day 14, Month 1.5, and Month 3 in MGS.
 - Proportion of patients with MGS score > 12 at Day 14, Month 1.5, and Month 3.
- MGYLS
 - Change from Baseline at Day 14 and Month 1.5 in MGYLS
- OSDI
 - Change from Baseline at Day 14 and Month 1.5 in OSDI total score.

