9.4.6 PLANNED INTERIM ANALYSES

Two official interim analyses are planned for Cohort 1 of the study. The first interim analysis is planned for after the 10th patient in Cohort 1, Group 3 exits the study. Only data collected up to the last patient exiting the study from Cohort 1, Group 3 will be included in the first interim analysis. All ongoing patients in Cohort 1 will remain masked until the second interim analysis.

A second interim analysis is planned after the final patient from Cohort 1 exits the study (Cohort 1, Group 4). Outcomes from this analysis will assist in the confirmation of the study drug concentration and frequency to be used for the Expansion Cohort.

One interim analyses is planned for the Expansion Cohort of the study. The interim analysis is planned for after the last enrolled patient completes the month 3 visit. Only data collected up to the month 3 visit will be included in the interim analysis. The primary endpoints for the US will serve as an Interim Analyses for the Month 6 primary endpoints. The sample size may be adjusted for power or to address any concerns for alpha inflation.

A final database lock will occur at the completion of the Expansion Cohort and the safety, tolerability, and efficacy data from Cohort 1 and the Expansion Cohort will be analyzed separately and in a combined fashion. At the final analysis, statistical significance will be declared for 2-sided p-values ≤ 0.05 .

Given the exploratory nature of Cohort 1 no adjustments for multiplicity will be applied across the primary or secondary endpoints in this cohort. Multiplicity will be controlled across the primary endpoints in the Expansion Cohort as described in Section 9.4.1.

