8.1.1. Primary Efficacy Endpoints

The primary efficacy variables are:

- change from baseline to Month 3 in MGYLS
- change from baseline to Month 3 in OSDI total score

The primary efficacy endpoints will be evaluated using the following hierarchical approach. For each endpoint, the subsequent endpoint will not be evaluated unless the prior endpoint is significant at $\alpha=0.05$. Therefore, this hierarchical approach controls for the family-wise Type I error and does not require adjustment for multiplicity, as per [Dmitrienko and D'Agostino, 2013](#).

- a) Change from baseline to Month 3 in MGYLS, comparing AZR-MD-001 0.5% to placebo.
- b) Change from baseline to Month 3 in OSDI total score, comparing AZR-MD-001 0.5% to placebo.
- c) Change from baseline to Month 3 in MGYLS, comparing AZR-MD-001 1.0% to placebo.
- d) Change from baseline to Month 3 in OSDI total score, comparing AZR-MD-001 1.0% to placebo.

Multiple imputation will be applied, as described in [Section 5.3](#). Analyses will be performed as follows.

Change from baseline in MGYLS will be analyzed at Month 3 using an ANCOVA model with (continuous) baseline MGYLS score as a covariate and treatment (AZR-MD-001 ointment/semi-

solid drug or placebo), duration of disease category (i.e., <5 or ≥ 5 years), and baseline MGS score category (< 6 or ≥ 6 and ≤ 12) as factors in the model. This ANCOVA model will also be performed for each AZR-MD-001 ointment/semi-solid drug dosing level versus placebo. The least square means for the differences between treatments will be presented along with two-sided (95%) confidence intervals.

The following pseudocode will be used:

```
PROC GENMOD data=xxx;  
  BY visit;  
  CLASS treatment (ref = 'AZR-MD-001 PLACEBO') duration baseMGS;  
  MODEL chg =treatment base duration baseMGS;  
  LSMEANS treatment;  
run;
```

Change from baseline in OSDI total score will be analyzed at Month 3 using the same methodology as the change from baseline in MGYLS, using an ANCOVA model with (continuous) baseline OSDI total score as a covariate and treatment, duration of disease category, and baseline MGS score category as factors in the model.

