8.2.1. Key Secondary Efficacy Analyses

Proportion of MGYLS responders based on change from baseline ≥ 5 will be analyzed through Month 3 using a CMH test to compare the proportions between each AZR-MD-001 group and placebo, stratifying by disease duration category (i.e., <5 or ≥ 5 years) and baseline MGS score category (<6 or ≥ 6 and ≤ 12). If the CMH statistic is not estimable, the treatment difference will be evaluated using Pearson's chi-square test, or Fisher's exact test (if the expected cell count is <5 for at least 25% of the cells).

The following pseudocode will be used:

```
PROC FREQ data=xxx;  
  BY visit;  
  TABLE baseMGS * duration * treatment * response/CMH;  
  ODS OUTPUT CMH = outcmh (where=(STATISTIC=2));
```

```
Run;

PROC FREQ data=xxx;
  BY visit;
  TABLE treatment * response/EXACT;
  ODS OUTPUT CHISQ = outc (where=(STATISTIC='Chi-Square'))
             FISHERSEXACT=outf (where=(NAME1='XP2_FISH'));
Run;
```

Proportion of OSDI responders based on OSDI total score <13 will be analyzed through Month 3 as described for the proportion of MGYLS responders, using a CMH test (or chi-square/Fisher's Exact if CMH is not estimable) to evaluate the difference between treatments, controlling for duration of disease category and baseline MGS score category.

Change from baseline in SPEED score at Day 14, Month 1.5 and Month 3 will be analyzed as described for MGYLS in [Section 8.1.1](#).

Change from baseline in Eye Dryness VAS at Day 14, Month 1.5 and Month 3 will be analyzed as described for MGYLS in [Section 8.1.1](#).

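### The 24 key secondary tests have no gate, order, alpha level or nominal label, so a key secondary result has no stated error rate behind it

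*SAP*

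**What the plan says.** SAP 3.1.2 separates a key tier from the remaining secondary endpoints, introduced by "The key secondary efficacy endpoints include". It contains four entries:

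- "Proportion of patients with a change from baseline in MGYLS score" of at least 5, at Day 14, Month 1.5 and Month 3
- "Proportion of patients with OSDI total score < 13 at Day 14, Month 1.5, and Month 3"
- "Change from Baseline at Day 14, Month 1.5, and Month 3 in SPEED"
- "Change from Baseline at Day 14, Month 1.5, and Month 3 for Eye Dryness VAS"

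SAP 8.2.1 analyses the two responder endpoints "using a CMH test to compare the proportions between each AZR-MD-001 group and placebo". It sends SPEED and Eye Dryness VAS to the model of SAP 8.1.1, which is fitted for each dose level against placebo.

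The multiplicity rule is in SAP 8.1.1: "The primary efficacy endpoints will be evaluated using the following hierarchical approach". Four steps follow, a) to d): MGYLS and OSDI at 0.5%, then MGYLS and OSDI at 1.0%, all at Month 3. Nothing comes after step d.

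Protocol 9.4.6 limits multiplicity control in the Expansion Cohort to the primary endpoints. The same section has a general rule: "At the final analysis, statistical significance will be declared for 2-sided p-values" at or below 0.05. SAP section 8 marks p-values from the safety follow-up (Month 4.5 and Month 6) as descriptive. It puts no such mark on the key secondary tests through Month 3. SAP section 12, which lists departures from the protocol, adds no rule for this tier.

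**The concern.** The amendment history (protocol 12.12) presents the Expansion Cohort as the first confirmatory study of the product. In that setting, a tier labelled key invites the reader to give its results more weight than an ordinary secondary endpoint. The plan supplies nothing to support that weight. It has no gate, so a key secondary could be called significant even if step a fails. It has no order, no alpha, and no statement that the p-values are nominal.

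Because the SAP does label the Month 4.5 and Month 6 p-values, its silence on Day 14 to Month 3 is easily read as permission to declare significance at 0.05 on each test. Any rule written after the Month 3 unmasking described in SAP 1.2 would be open to the charge that the data chose it.

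**Working it through.** **Inputs.** Four endpoints and three visits (SAP 3.1.2); two dose contrasts (SAP 8.2.1); two-sided 0.05 (protocol 9.4.6, applied here to these tests); 1:1:1 allocation with a shared placebo arm (SAP 2.4), which gives a correlation of about 0.5 between the two dose contrasts. The documents give no correlations between visits or endpoints, so those are assumptions shown as ranges. Test statistics are treated as multivariate normal, with 400,000 draws per scenario.

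**The plan's own figure.** In a fixed sequence at 0.05 per step, a family-wise error occurs only if the first true null reached is rejected. The family-wise rate for a) to d) is therefore at most 0.05, as SAP 8.1.1 states (simulated 0.0501 under the global null).

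**Key secondary family, all nulls true.** Number of tests: 4 x 3 x 2 = 24. Expected false positives: 24 x 0.05 = 1.2.

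Under independence:
- either direction: 1 - 0.95^24 = 0.708
- favouring the drug only: 1 - 0.975^24 = 0.455

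With correlation:

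| Assumed correlation | Either direction | Favouring drug only |
|---|---|---|
| Common 0.1 | 0.69 | 0.40 |
| Common 0.2 | 0.65 | 0.36 |
| Common 0.3 | 0.60 | 0.31 |
| Common 0.4 | 0.53 | 0.27 |
| Common 0.5 | 0.46 | 0.23 |
| Common 0.6 | 0.38 | 0.19 |
| Dose 0.5, visit 0.3, endpoint 0.3 | 0.64 | 0.36 |
| Dose 0.5, visit 0.5, endpoint 0.3 | 0.60 | 0.33 |
| Dose 0.5, visit 0.7, endpoint 0.5 | 0.50 | 0.26 |
| Dose 0.5, visit 0.7, endpoint 0.6 | 0.47 | 0.24 |

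The either-direction figure crosses one half at a common correlation of about 0.44.

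**Month 3 only (4 x 2 = 8 tests, dose correlation 0.5).** Either direction: 0.32, 0.30 and 0.27 for endpoint correlations 0, 0.3 and 0.5. Favouring the drug only: 0.17, 0.15 and 0.14.

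**Some endpoints truly respond.** If two of the four respond at both doses, 2 x 3 x 2 = 12 nulls remain. Independence gives 1 - 0.95^12 = 0.46 in either direction and 1 - 0.975^12 = 0.26 favouring the drug. With visit correlation 0.3 to 0.7 and endpoint correlation 0.3 to 0.5, the ranges are 0.33 to 0.41 and 0.17 to 0.22.

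**After the fix.** Eight Month 3 tests in fixed sequence after step d keep the family-wise rate at 0.05 (simulated 0.0503 for the eight alone).

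**What the gate costs.** Step d compares OSDI at 1.0% with placebo. The difference is 5.33 - 0.81 = 4.52 (SAP Table 1). With the pooled SD of 8.71 from SAP 2.3.2 and 75 per arm, the noncentrality is 4.52 / (8.71 x sqrt(2/75)) = 3.18, and the two-sample t-test has power 0.884. The same method returns the SAP's 0.918 for MGYLS at 0.5%. With the arm-specific SDs of Table 1 (8.39 and 6.31) and 72 per arm, power for step d is 0.952.

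**The case against.** The strongest reply is that the plan never claims otherwise. Both documents openly confine error control to the primary endpoints, and neither says a key secondary will support a confirmatory statement. The protocol has no key tier at all, and the SAP does not define the term. The 0.05 sentence in protocol 9.4.6 concerns the final analysis after the final database lock, and the SAP sets no threshold for secondary tests. Applying 0.05 to the 24 tests is therefore an inference. All of this stands, and it keeps the point from being a contradiction or a breach of a stated error rate.

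A reader might also infer that a false positive is more likely than not. The documents do not support that. It needs all 24 nulls to be true, results favouring placebo to count, and correlations below about 0.44, which the documents do not give. Repeated visits on overlapping symptom scales could exceed that value. A falsely favourable result stays below one half throughout. The complete null is also a hard case: two of the four endpoints dichotomise the primary variables, so if the primary effects are real those nulls are unlikely to hold.

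Nor should the Phase 3 confirmatory wording in SAP 1.1 be read as a claim about these endpoints. It sets a production and quality-control standard, and the protocol synopsis labels the study Phase 2a. The amendment history is the better source for the cohort's confirmatory purpose.

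These replies limit the size of the concern. They do not supply the missing rule or label.

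**Conclusion.** The gap is real: 24 key secondary tests stand outside the only error-controlled sequence, with no gate and no nominal label. Under the complete null, the 71% figure needs independence. The 46% to 65% range rests on assumed common correlations of 0.5 down to 0.2. The ceiling of about 46% for a falsely favourable result is also the independence value and falls with positive correlation. The Month 3 range of 27% to 32% assumes endpoint correlations of 0.5 down to 0. All of these are well above the 5% that a fixed sequence would give.

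The consequence is confined to how key secondary results may be described. The primary tests and their error rate are unaffected. This is a low-cost improvement that should be made, and matters most if the sponsor intends any claim on these endpoints.

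**What to change.** In SAP 8.2.1, before the Month 3 unmasking, state that after step d the fixed sequence continues at two-sided 0.05 with the Month 3 key secondary tests in the order of SAP 3.1.2, taking 0.5% then 1.0% within each endpoint:

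1. MGYLS change of at least 5
2. OSDI below 13
3. SPEED change
4. Eye Dryness VAS change

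Label all Day 14 and Month 1.5 key secondary p-values nominal. If the sponsor wants no confirmatory claim on these endpoints, one sentence labelling every key secondary p-value nominal closes the gap instead.

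The text cost is one paragraph, and the alpha and power of steps a) to d) do not change. The statistical cost is that every key secondary after the first non-significant step becomes descriptive. In particular, all 0.5% key secondaries then depend on both 1.0% primary tests succeeding. For OSDI at 1.0% that power is about 0.88 at SD 8.71 and 75 per arm. SAP 2.3.2 gives above 0.999 for this comparison, which the calculation does not reproduce, so that figure should be checked before the order is settled. A 0.5% test late in the list also depends on the 1.0% tests of the endpoints before it. The nominal-label option avoids these dependencies but gives up any confirmatory use of the tier.

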5.1 INCLUSION CRITERIA

- Male or female, 18 years of age or older at screening visit
- Capable of understanding and willing to provide written informed consent and likely to complete the entire course of study according to instructions
- Written authorization for use and release of health and research study information has been obtained
- Best-corrected visual acuity (BCVA) of 20/40 or better (Snellen equivalent), using the logarithm of the minimum angle of resolution (LogMAR) in each eye at the screening and baseline visits
- Evidence of meibomian gland obstruction (based on a meibomian gland secretion (MGS) score of ≤ 12 for 15 glands of the lower lid) in both eyes at the screening and baseline visits
- Reported dry eye signs and symptoms within the past 3 months
- Prior to starting screening visit procedures, patients are required to have discontinued:
 - Use of systemic antihistamines or isotretinoin for at least 1 month
 - Anti-inflammatory treatments for DED (e.g., cyclosporine ophthalmic emulsion [Restasis® or Ikervis®] or lifitegrast ophthalmic solution [Xiidra®]) for at least 3 months
 - All other prescription medications used for dry eye or MGD (e.g., antibiotics, corticosteroids, and non-steroidal anti-inflammatory drugs) for at least 2 weeks
 - LipiFlow® or other lid-heating therapy, meibomian gland probing, or therapeutic gland expression in either eye within 6 months prior to the screening visit
 - All other MGD treatments (e.g., at-home warm compress therapy, eyelid hygiene, eyelid massage, and manual lid expression) for at least 2 weeks
- And
 - All other topical ophthalmic preparations (including artificial tear substitutes) other than the study drops: 72 hours prior to screening visit. If artificial tear substitutes were used within 72 hours of the screening visit the visit should be rescheduled
- Evidence of MGD at the screening and baseline visits:
 - Score ≥ 6 on the Standard Patient Evaluation of Eye Dryness questionnaire (SPEED)
 - Ocular Surface Disease Index (OSDI) questionnaire score ≥ 13 and < 34
- And
 - TBUT < 10 seconds in both eyes

- Demonstrated ability to follow dosing instructions at the baseline visit
- A negative pregnancy test result for all women of childbearing potential at the screening visit

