3.1.3. Exploratory Efficacy Endpoints

3.1.3.1. Exploratory Efficacy Endpoints Evaluated At Month 3

- MGYLS
 - Proportion of patients with MGYLS >2 at Day 14, Month 1.5, and Month 3.
- Meibomian Glands Yielding Optimal Liquid Secretion (MGYOLS, e.g., number of expressible glands yielding clear meibum)
 - Change from Baseline at Day 14, Month 1.5, and Month 3 in MGYOLS.
 - Proportion of patients with MGYOLS score >2 at Day 14, Month 1.5, and Month 3.
- OSDI total score and subscales
 - Proportion of patients with OSDI total score Decrease from Baseline >4.5 at Month 3 (4.5 is the minimally important clinical difference for early to moderate disease).
 - Change from Baseline at Day 14, Month 1.5, and Month 3 in OSDI subscales
- SPEED
 - Proportion of patients with SPEED <6 at Day 14, Month 1.5, and Month 3
- TBUT
 - Change from Baseline at Day 14, Month 1.5, and Month 3 in TBUT.
 - Proportion of patients with TBUT score >5 at Day 14, Month 1.5, and Month 3.
 - Proportion of patients with TBUT score >10 at Day 14, Month 1.5, and Month 3.
- Schirmer's Test without Anesthesia
 - Change from Baseline at Day 14, Month 1.5, and Month 3 in Schirmer's test.
 - Proportion of patients with Schirmer's test result ≥ 10 mm at Day 14, Month 1.5, and Month 3.
- VAS
 - Change from Baseline at Day 14, Month 1.5, and Month 3 in individual VAS results (besides eye dryness), Average VAS, and Worst VAS, separately.
 - Proportion of patients with score decreased by ≥ 5 , separately for Average VAS and Worst VAS, at Day 14, Month 1.5, and Month 3.
- Other
 - Eyelid margin erythema/telangiectasias at Day 14, Month 1.5, and Month 3.
 - Corneal and conjunctival staining (0 to 5 scale) at Day 14, Month 1.5, and Month 3.

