5.2.6. Ocular Surface Disease Index Total Score and Subscale Scores

The OSDI questionnaire, provided in [Appendix 2](#), consists of 12 questions regarding ocular symptoms, environmental triggers, and vision-related functioning in patients with DED. The patient will be asked to rate each symptom using a 5-point scale (0 to 4), where 0 = none of the time; 1 = some of the time; 2 = half of the time; 3 = most of the time; and 4 = all the time. There are 7 questions related to visual functioning that allow a response of “N/A” (not applicable).

The OSDI total score (on a scale of 0 to 100) is calculated from the raw scores of each of the 12 questions based on the formula: $([\text{sum of scores for all questions answered}] \times 100) / ([\text{total number of questions answered}] \times 4)$, where questions answered with N/A are considered unanswered and excluded from the calculation. Higher scores represent greater disability.

Subscale scores are calculated similarly, where the Ocular Symptoms subscale includes the 5 questions on light sensitivity, gritty feeling, painful/sore eyes, blurred vision, and poor vision; the Vision Related Function subscale includes the 4 questions on problems reading, driving at night, working with a computer, or watching TV; and the Environmental Triggers subscale includes questions about windy conditions, low humidity, and air conditioning.

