Change from baseline in Average VAS and Worst VAS at Day 14, Month 1.5 and Month 3 will be analyzed as described for MGYLS in [Section 8.1.1](#).

Proportion of Average VAS responders based on decrease ≥ 5 and proportion of Worst VAS responders based on decrease ≥ 5 will be analyzed through Month 3 as described for the proportion of MGYLS responders, using a CMH test (or chi-square/Fisher's Exact if CMH is not estimable) to evaluate the difference between treatments, controlling for duration of disease category and baseline MGS score category.

Change from Schirmer's assessment at Day 14, Month 1.5 and Month 3 will be analyzed as described for MGYLS in [Section 8.1.1](#).

Proportion of Schirmer's ≥ 10 mm responders will be analyzed through Month 3 as described for the proportion of MGYLS responders, using a CMH test (or chi-square/Fisher's Exact if CMH is not estimable) to evaluate the difference between treatments, controlling for duration of disease category and baseline MGS score category.

Change from baseline in Burning/Stinging VAS, Itching VAS, Foreign Body Sensation VAS, Eye Discomfort VAS, Photophobia VAS, and Pain VAS at Day 14, Month 1.5 and Month 3 will be analyzed as described for MGYLS in [Section 8.1.1](#).

Proportion of patients with clinical cure, defined as having MGYLS change from baseline ≥ 5 and OSDI total score < 13 , will be analyzed through Month 3 as described for the proportion of MGYLS responders, using a CMH test (or chi-square/Fisher's Exact if CMH is not estimable) to evaluate the difference between treatments, controlling for duration of disease category and baseline MGS score category.

Eyelid margin erythema and telangiectasias results will be summarized by time point, in conjunction with other findings from the slit lamp examination. Actual values and shifts from baseline through Month 3 will be summarized by parameter and time point. Changes from baseline will be analyzed at each time point using CMH statistics to evaluate the differences between each AZR-MD-001 treatment group and placebo, controlling for baseline value, using the following pseudocode:

```
PROC FREQ data=xxx;
  BY visit;
  TABLE treatment * base * result / CMH;
  ODS output CMH=outcmh (where=(ALTHYPOTHESIS='General Association'));
run;
```

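### The key secondary OSDI < 13 responder test omits baseline OSDI, although its cut-off sits at the entry floor and the chance of response depends strongly on the baseline score

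*SAP*

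**What the plan says.** Protocol 5.1 requires, at screening and at baseline, "Ocular Surface Disease Index (OSDI) questionnaire score ≥ 13 and < 34". SAP 3.1.2 makes "Proportion of patients with OSDI total score < 13 at Day 14, Month 1.5, and Month 3" a key secondary endpoint and sets no minimum change.

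On the analysis, SAP 8.2.1 states "Proportion of OSDI responders based on OSDI total score <13 will be analyzed through Month 3", by a CMH test "controlling for duration of disease category and baseline MGS score category". The pseudocode given for the MGYLS responders, whose method this endpoint follows, is "TABLE baseMGS * duration * treatment * response/CMH". Baseline OSDI appears in neither the text nor the code. By contrast, the primary OSDI change analysis in SAP 8.1.1 has continuous baseline OSDI total score as a covariate, alongside the same two randomisation factors.

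The < 13 rule recurs in two places. SAP 8.3.1 tests the "Proportion of patients with clinical cure, defined as having MGYLS change from baseline ≥ 5 and OSDI total score < 13". SAP 8.3.2 repeats both the OSDI responder and the cure analysis at Months 4.5 and 6. A separate exploratory responder, a decrease of more than 4.5 points, is in SAP 3.1.3.1, where the SAP notes that "4.5 is the minimally important clinical difference for early to moderate disease".

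**The concern.** When a responder threshold lies at the edge of the eligible range, distance from the threshold at entry largely determines who can cross it. A patient who enters just above 13 needs a small fall, and one who enters near 34 needs a very large one. Baseline OSDI should therefore be a strong predictor of this binary outcome.

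Leaving a strong predictor out of a randomised comparison does not bias it, but has two costs. A chance difference between arms in baseline OSDI passes directly into the responder difference, and the unexplained variation can reduce power. The SAP already accepts baseline OSDI as a covariate for the continuous form of the same score and gives no reason for dropping it here.

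**Working it through.** **The plan's own OSDI figures.** The documents give no expected rate or power for the < 13 responder. The nearest figure is protocol 9.1.2: 58 per group, 90% power, difference 4.52, SDs 6.31 and 8.34.
- Pooled SD = √((6.31² + 8.34²)/2) = 7.395.
- n = 2 × (1.960 + 1.282)² × (7.395/4.52)² ≈ 56.3, so 57 by the normal formula and 58 by the t-test. It reproduces.

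**Inputs.** SAP 5.2.6: 12 items scored 0 to 4, total = 100 × sum/(4 × items answered). SAP Table 1, OSDI change at Month 3, mean (SD): placebo −0.81 (6.31), 1.0% −5.33 (8.39), 0.5% −8.36 (9.06). SAP 2.3.1: 75 per arm.

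**Assumptions not in the documents.** Baseline uniform over the eligible 12-item scores, normally distributed changes, complete data, and randomisation strata unrelated to OSDI.

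**Required fall.** With 12 items answered, one category is 100/48 = 2.08 points. There are ten eligible scores, from 7/48 (14.58) to 16/48 (33.33). The highest score below 13 is 6/48 = 12.50. The required fall is 14.58 − 12.50 = 2.08 at the bottom and 33.33 − 12.50 = 20.83 at the top, or one to ten categories.

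**Response by baseline.** P(OSDI < 13 at baseline b) = Φ((13 − b − mean)/SD), with change independent of baseline. For placebo at 14.58 this is Φ((13 − 14.58 + 0.81)/6.31) = Φ(−0.12) = 45%.

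| Baseline | Placebo | 1.0% | 0.5% |
|---|---|---|---|
| 14.58 | 45% | 67% | 77% |
| 22.92 | 7% | 29% | 43% |
| 33.33 | 0.1% | 4% | 9% |
| Uniform average | 12.7% | 29.6% | 40.7% |

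The modelled differences from placebo are 16.9 points (1.0%) and 28.0 points (0.5%).

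**Chance imbalance.** The SD of the ten scores is 5.98, so the between-arm difference in mean baseline has SD 5.98 × √(2/75) = 0.98, about one point. Between the lowest and highest scores, the response rate falls by (45.1 − 0.1)/18.75 = 2.4 percentage points per OSDI point on placebo and (67.2 − 3.7)/18.75 = 3.4 on 1.0%. A one-point imbalance thus moves the difference by roughly 2 to 3 percentage points.

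**Power, by simulation of the CMH test (75 per arm).** Slope 0.6 means that the expected fall grows by 0.6 points per point of baseline.

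| Comparison and scenario | Planned (4 strata) | Plus two-level OSDI, split at 23.5 (8) | Plus four-level OSDI, crossed (16) |
|---|---|---|---|
| 1.0%, slope 0 | 0.71–0.73 | 0.77–0.78 | about 0.78 |
| 1.0%, slope 0.6, Table 1 SD as residual | 0.91 | 0.92 | 0.90 |
| 1.0%, slope 0.6, total SD held at Table 1 | 0.97 | 0.97 | 0.965 |
| 0.5%, slope 0 | 0.98 | 0.99 | not needed |

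At slope 0, a logistic model with baseline OSDI gave about 0.82 for 1.0%. Under the null, the planned CMH rejected in 4.3% to 4.5% of runs and the logistic model in 5.3%, all close to 5%.

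**The case against.** The other side has four good points.

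- **Validity is not in question.** A reader might infer that baseline position decides the treatment comparison. It does not: randomisation balances baseline OSDI in expectation and the error rate holds. Baseline governs individual status and absolute rates. A typical chance imbalance moves the contrast by 2 to 3 points against modelled effects of 17 and 28.
- **The threshold is less trivial than it looks.** A reader might infer that one category on one item generally makes a responder. That is true only at the lowest of the ten eligible 12-item scores; the others need two to ten categories. Only the two lowest (falls of 2.08 and 4.17) allow response with a fall below 4.5.
- **The definition answers its own question.** A reader might conclude that a fall above 4.5 should be built into the responder rule. The documents do not require this. Reaching a score below the entry range is a different question from improving by a meaningful amount, and the SAP already covers the latter through the primary change analysis and the separate > 4.5 responder. A combined rule would still count large improvers from high baselines as failures. It is a choice of endpoint, not a correction.
- **The stakes are limited.** The hierarchy in SAP 8.1.1 covers only the four primary tests, so no alpha-controlled claim rests on this endpoint. Clinical cure is exploratory and also needs an MGYLS gain of at least 5.

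All four stand, and they set the size of the point. They do not explain why a strong predictor that is already collected, and already used for the primary OSDI analysis, is left out here.

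**Conclusion.** The point holds as a matter of efficiency and robustness, not of validity. The OSDI < 13 cut-off coincides with the entry floor, the required fall varies tenfold across eligible patients, and the planned test ignores the variable that determines it.

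Under uniform baselines and changes independent of baseline, the omission costs about 5 percentage points of power for 1.0% versus placebo relative to a two-level stratum. For 0.5% there is little to gain. If larger falls occur at higher baselines (slope 0.6), the gain is about nil. The documents give neither the baseline OSDI distribution nor this slope, so the power figures illustrate a range rather than forecast a result. The tenfold range in required fall and the missing covariate depend on none of these assumptions, apart from all 12 items being answered.

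**What to change.** In SAP 8.2.1, add a two-level baseline OSDI category (for example < 23.5 versus ≥ 23.5, which splits the ten eligible 12-item scores five and five) to the CMH strata for the OSDI < 13 analysis. Alternatively, use a model with continuous baseline OSDI plus the two randomisation factors. The first keeps the CMH approach chosen in SAP section 12; the second would mean returning to a regression model for this endpoint.

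Apply the same change to clinical cure in 8.3.1, and to the OSDI < 13 and cure analyses at Months 4.5 and 6 in 8.3.2, so that one rule has one analysis throughout. Make it before unmasking.

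Do not cross four OSDI levels with the existing four strata. That gives 16 cells of about nine patients each (150/16) per pairwise test, adds little over two levels, and falls slightly below the planned test at slope 0.6.

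Keep the < 13 definition and present it beside the planned > 4.5-point responder.

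The cost is SAP wording, one more variable in the code and smaller strata (about 19 patients per cell with eight), with little or no gain if change depends strongly on baseline. No new data are needed.
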